Objectives:	
Principal aim: SAFETY
 
The primary objective of the study is to confirm the safety of a marketed auricular spray with reverse and microdiffusion nozzle by clinical examination by ENT specialist and by the scoring of the irritation of the ear canal at D60 in comparison with basal scoring of irritation at D0 (scale 0 to 3) such as:
 
 
- 0: no irritation,
 
- 1: slight irritation (located slight erythema and/or dryness),
 
- 2: moderate irritation (clear erythema or dryness which may be visible on the whole treated area),
 
- 3: severe irritation (serious erythema with potential oedema and/or scar).
 
 
Potential adverse events collection.
 
Secondary aims: EFFICACY/PERFORMANCE PREVENTION for investigational device with reverse nozzle, investigational device with microdiffusion nozzle and for control group, in comparison to the baseline (D0) and between groups:
 
 
• scoring of the obstruction of ear canal by the Investigator
 
 
0: no obstruction – normal and/or no significant presence of cerumen in the ear canal. The membrane is clearly visible.
 
1: <25% minimal, very little and mostly insignificant impacted cerumen. The tympanic membrane is visible, but with still a little bit cerumen.
 
2: 25-50% mild, some excessive impacted cerumen causing partial occlusion of the ear canal. The tympanic membrane is not entirely visible, quite difficult to see.
 
3: 50-75% moderate, moderate and excessive impacted cerumen causing partial occlusion of the ear canal. Partial to very little of the tympanic membrane is visible.
 
4: 75-100% severe, severe and excessive impacted cerumen causing partial or complete occlusion of the ear canal. Little if any of the tympanic membrane is visible.
 
 
• audiogram with classification of the loss or gain hearing function using the following scale (only for subjects more than 6):
 

YSLAB	Medical Device CIP #23E1670	Final version 2.0 Date: 09/11/2023	Confidential Page 11/64
-------	--------------------------------	---------------------------------------	----------------------------

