	
No hearing function loss, hearing function loss between 5 to 10dB, hearing function >10dB (Subha et al.2006), hearing function win between 5 to 10 dB, hearing function win >10dB.
 
Additionally, the secondary objective of this study will be to see if the investigational device is more efficient in children, adults or elderly subjects (for both nozzles - reverse or microdiffusion).
 
 
• Subject's self-evaluation using a questionnaire.
 
• Evaluation of the effect on the number of auricular affection (such as otitis) during the use period (daily log).
 

Design:	Open study, randomized, before / after treatment, with tested product versus control group, in parallel groups
Planned Sample Size:	
99 included subjects and results delivered on 90 subjects.
 
 
• 1 group of 72 included subjects in order to have results on 66 subjects (33 subjects using product with the "reverse diffuser" and 33 using the product with the "microdiffusion diffuser")
 
• 1 group of 27 included subjects in order to have results on 24 subjects not using a spray (control group). (in case of discomfort or pain, they are allowed to use ear drops prescribed by a doctor after a medical examination)
 

Number of investigational study sites:	2 centers
Inclusion criteria:	
 
1. Gender: female and/or male.
 
2. Age: 
 
- 30 to 40% having age between 3 to 12 yo,
 
- 30 to 40% between 13 to 65 yo,
 
- 30 to 40% more than 65 yo.
 
 
 
3. Subjects able to use the tested product.
 
4. Subjects having history of cerumen occlusion more than once a year with or without symptoms (reduction of hearing function, obstruction feeling of the ear canal,..).
 
5. Subjects having ear help system or regular users of systems such as anti-noise plugs or headsets (only for the 13yo subjects and more).
 
6. Subjects having a clinical score of ear canal obstruction of 2 or 3 at D0.
 

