Statistical methods:	
The analysis of the primary endpoint will be performed on the ITT and population.
 
The analysis of the secondary endpoint will be performed on the population.
 
The analysis of the safety/tolerance parameters will be performed on "safety" population.
 
Primary endpoint:
 
The irritation is assessed by the Laryngologist using a 4-point structured scale (from "No irritation (0)" to "Severe irritation (3)" on D0 and D90).
 
For each product, a paired t-test will be used to test whether the change from baseline (D90-D0) differ significantly from 0. The normality assumption will be checked using a Shapiro-Wilk test (<math>\alpha=0.01</math>), in case of rejection, a Wilcoxon signed ranks test will be used.
 
To test whether the products differ statistically in terms of change from baseline (D90-D0), a two-sided t-test is used. If the normality assumption is not met, a non-parametric approach is used with a Wilcoxon signed rank test.
 
Secondary endpoints:
 
For each secondary parameter:
 
 
• Clinical score of the irritation with structured scale
 
• Clinical score of the obstruction of ear canal
 
• Results of audiogram with classification of the loss or win hearing function.
 
• The number of auricular affection (such as otitis) during the use period
 
 
For each product, a paired t-test will be used to test whether the change from baseline (D90-D0) differ significantly from 0. The normality assumption will be checked using a Shapiro-Wilk test

YSLAB	Medical Device CIP #23E1670	Final version 2.0 Date: 09/11/2023	Confidential Page 13/64
-------	--------------------------------	---------------------------------------	----------------------------

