	
(<math>\alpha=0.01</math>), in case of rejection, a Wilcoxon signed ranks test will be used.
 
To test whether the products differ statistically in terms of change from baseline (D90-D0), a two-sided t-test is used. If the normality assumption is not met, a non-parametric approach is used with a Wilcoxon signed rank test.
 
For the subjective evaluation questionnaire:
 
For each item of the subjective questionnaire, the raw data will be summarized in frequency (N) and percentage (%) by group of product.
 
All statistical tests will be assessed at <math>\alpha = 5\%</math> level of significance in a bilateral approach.
 
Statistical software: SAS® v9.4.

Foreseen study duration:	
Clinical investigation beginning: Q4 2023
 
Clinical investigation end: Q3 2024
 
Clinical investigation global duration: 8 months
 
Duration by subject: 90 days

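### Cheap improvement: the between-group tests subtract the D0 score but do not adjust for it; fitting D0 as a covariate would usually narrow the comparison, by an amount the documents do not let us fix

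*Combined protocol and SAP*

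**What the plan says.** All references are to the overall synopsis (section 1.5) and the flow-chart, the only parts available for this review.

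- **Outcome.** "The irritation is assessed by the Laryngologist using a 4-point structured scale", at D0 and D90.
- **Between-group test, primary endpoint.** "To test whether the products differ statistically in terms of change from baseline (D90-D0"), the plan uses a two-sided t-test. The fallback reads: "If the normality assumption is not met, a non-parametric approach is used with a Wilcoxon signed rank test". The same text is repeated under Secondary endpoints. No covariate, model or stratification factor is named. Tests are at the 5% "level of significance in a bilateral approach".
- **Primary objective.** Irritation is judged "in comparison with basal scoring of irritation at D0 (scale 0 to 3"). The objective itself names no between-group contrast; comparison between groups is announced under the secondary aims. The statistical methods nevertheless place a between-group test under the primary endpoint.
- **Entry.** "Subjects having a clinical score of ear canal obstruction of 2 or 3 at D0". There is no such restriction on irritation.
- **Size.** "1 group of 72 included subjects in order to have results on 66 subjects" (33 per nozzle) and "1 group of 27 included subjects in order to have results on 24 subjects not using a spray (control group").
- **Data available.** The flow-chart schedules irritation scoring and the audiogram at both visits. Age is recruited in three quota bands, at two centres.

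**The concern.** Subtracting D0 in full is the best use of it only when the regression slope of D90 on D0 is 1. When the slope is lower, the change score carries D0 noise into the comparison. Bounded scales add a second problem: a subject at irritation 0 can only worsen and one at 3 can only improve, so the change depends on where the subject started. Randomisation makes the change-score contrast unbiased on average. In a single small trial, however, a chance difference in D0 between arms feeds into it. Conditioning on D0 deals with this; subtraction does not.

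Precision is what is at stake. For a safety comparison the width of the interval matters more than the p-value, because a non-significant difference with a wide interval gives little reassurance.

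**Working it through.** **1. The plan's own figures.** 72 + 27 = 99 included and 66 + 24 = 90 evaluable, so the totals agree. The synopsis gives no effect size, SD or power, so no power calculation can be reproduced.

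**2. What these arms can detect.** For 80% power at two-sided 5%, the detectable difference in SDs of the change is (1.960 + 0.842) × √(1/n₁ + 1/n₂):
- 33 v 33: 2.802 × 0.246 = 0.69
- 33 v 24: 2.802 × 0.268 = 0.75
- 66 v 24: 2.802 × 0.238 = 0.67

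Only fairly large differences are detectable, so precision matters.

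**3. Variance of the D0-adjusted comparison relative to raw change.** Let k = SD(D0)/SD(D90) and r = the D0–D90 correlation. Then

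ratio = (1 − r²) / (1 + k² − 2rk) = (1 − r²) / [(1 − r²) + (k − r)²].

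The ratio never exceeds 1 in large samples, and equals 1 when r = k. With k = 1 it reduces to (1 + r)/2:

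| r | ratio | variance reduction |
|---|---|---|
| 0.3 | 0.65 | 35% |
| 0.5 | 0.75 | 25% |
| 0.7 | 0.85 | 15% |
| 0.9 | 0.95 | 5% |

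For an assumed difference of 0.6 SD of the change and r = 0.3, 0.5 and 0.7, power rises from 61% to 79%, 73% and 68% at 33 v 24, and from 68% to 86%, 80% and 75% at 33 v 33.

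**4. Does irritation gain more than obstruction?** The formula was applied to simulated scores with assumed distributions, at latent correlations 0.3 to 0.7:

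| Assumed scores | ratio |
|---|---|
| Irritation, all 0 at D0 | 1.00 |
| Irritation, 95% at 0 on D0; 85/12/3% at 0/1/2 on D90 | 0.89–0.99 |
| Irritation, 85/12/3% at both visits | 0.58–0.75 |
| Irritation, D0 spread over 0–3, D90 near the floor | 0.24–0.26 |
| Obstruction, D0 at 2 or 3, wide D90 | 0.96–1.00 |
| Obstruction, D0 at 2 or 3 (50/50), narrow D90 | 0.76–0.93 |

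The ranges overlap and the order can go either way.

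**5. Simulated trials at 33 v 24.** Assumed D0 irritation shares were 70/20/8/2%, with a latent shift of 0.6 SD. Fitting D0 alone lowered the variance by about 32%, 22% and 10% at latent r = 0.3, 0.5 and 0.7. Against a rank test of the change, rank ANCOVA on D0 raised power from 35 to 46%, 43 to 51% and 56 to 59%.

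**6. Cost of extra terms.** Uninformative covariates inflate variance by about 1 + p/(n − g − p − 1), with p covariate parameters and g arms.
- D0 only, n = 57: 1 + 1/53 = 1.019. With k = 1, the gain is used up at r = 2/1.019 − 1 = 0.96.
- D0, age band (2 parameters) and centre, n = 57: 1 + 4/50 = 1.08. The gain is used up at r = 2/1.08 − 1 = 0.85.
- The same four parameters cost 1 + 4/59 = 1.07 at n = 66 and 1 + 4/82 = 1.05 at n = 90.

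Simulation with non-prognostic age and centre agreed: at latent r = 0.85 the variance was 3 to 6% higher than for raw change. With 95% at 0 on D0, power under this larger model went from 13 to 13%, 13 to 13%, 19 to 16% and 22 to 18% at latent r = 0.3, 0.5, 0.7 and 0.85.

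**7. Which test would be run.** In simulated irritation samples of 33 (latent r = 0.5), Shapiro-Wilk at 0.01 rejected normality of the change in 89 to 100%. The rank fallback is therefore the likely analysis. Obstruction was not simulated for this check, but its change also takes only a few integer values.

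**The case against.** The strongest reply is that the planned contrast is valid under randomisation, so this is an efficiency preference and not an error. That stands, and it limits the point to a cheap improvement. A second reply is that the primary objective is a comparison with D0, which adjustment leaves untouched. That also stands for the paired tests, but the between-group test is listed under the primary endpoint and is a planned analysis. A third is that gains quoted against a t-test are beside the point if the rank fallback is used; step 5 shows a gain against the rank test too.

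Four stronger readings might be inferred, and the documents support none of them:
- *The plan ignores D0.* It does not: the outcome is D90 minus D0. What is missing is D0 as a covariate.
- *The loss is greatest for irritation, because only obstruction is restricted at entry.* The absence of a restriction does not show that irritation varies at D0. If nearly all ear canals score 0, obstruction could gain more. For hearing, a high correlation over 90 days would leave little to gain.
- *Age band and centre should also be in the model.* Age bands are recruitment quotas; neither factor is stated to be a randomisation stratum or prognostic, and uninformative terms use up part of the gain.
- *There is no downside.* Step 6 shows there can be one.

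**Conclusion.** The point holds as an efficiency improvement. The between-group tests in the synopsis leave D0 out as a covariate, although it is already collected, in a trial whose arms detect only about 0.7 SD. Adjustment would usually narrow the interval and would account for chance D0 imbalance.

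Its size rests on assumptions about the SDs, the D0–D90 correlation and the D0 distribution. A reduction of 15 to 35% applies with equal SDs and r between 0.3 and 0.7. It is near zero at high r with equal SDs, and nil if all D0 scores are 0. With about 95% at 0, power may not rise and can fall a little. The variance ratios describe a linear model; for an ordinal or rank-based method they are a guide only. A fuller statistical section elsewhere in the plan could already cover this and should be checked first.

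**What to change.** For irritation and for obstruction, replace the between-group test of D90-D0 with one prespecified comparison of D90 adjusted for D0.

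- **Method.** Name one ordinal or rank-based method in advance, so that the choice does not hang on a Shapiro-Wilk result. One option is a proportional-odds model with arm and D0, which gives an adjusted odds ratio with a 95% CI. Another is rank ANCOVA on D0; if that is chosen, state which effect estimate and 95% CI go with it.
- **Contrasts.** State which arms are compared: nozzle v nozzle, each nozzle v control, or both.
- **Age band and centre.** Optional. Include them only if they are randomisation strata or expected to be prognostic.
- **Hearing.** Keep the stated classification of loss or gain. A D0-adjusted analysis in dB may be added as supportive.
- **Within-group tests.** Leave the paired tests against D0 as they are.

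This also removes the signed rank test from the comparison of independent groups, where it does not apply. Separately, the primary objective refers to D60 and the methods and flow-chart to D90; these must be reconciled.

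**Cost.** SAP wording and a few lines of SAS, with no new data or visits. The price is a model assumption, one degree of freedom for D0 (about 2% of variance), and some power loss if D0 and D90 are very highly correlated or nearly all D0 scores are 0.

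### The non-parametric fallback for comparing the products is a paired test, but the groups are independent; the rank-sum test should be named

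*Combined protocol and SAP*

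**What the plan says.** All references are to the synopsis, section 1.5.

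- **Design:** "Open study, randomized, before / after treatment, with tested product versus control group, in parallel groups".
- **Planned Sample Size:** results are wanted on 33 subjects with the reverse diffuser, 33 with the microdiffusion diffuser, and a control group described as "1 group of 27 included subjects in order to have results on 24 subjects not using a spray (control group").
- **Objectives:** the principal aim is irritation "in comparison with basal scoring of irritation at D0". The secondary efficacy aims are to be assessed "in comparison to the baseline (D0) and between groups".
- **Statistical methods, within product:** a paired t-test on D90-D0, with a Shapiro-Wilk check at 0.01 and a Wilcoxon signed ranks test if normality is rejected.
- **Statistical methods, between products:** the paragraph opens "To test whether the products differ statistically in terms of change from baseline (D90-D0"), names a two-sided t-test, and continues "If the normality assumption is not met, a non-parametric approach is used with a Wilcoxon signed rank test". The same paragraph appears under the primary endpoint and again under the secondary endpoints.

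No rank-sum, Mann-Whitney or Kruskal-Wallis test is named anywhere in the supplied text.

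**The concern.** The signed rank test ranks the absolute values of one set of differences and asks whether they are symmetric about zero. Within a product this fits, because each subject supplies a D0 and a D90 score. Between products it does not: each subject belongs to one group, and nothing links a subject in one group to a subject in another.

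An analyst who reaches the fallback must therefore depart from the plan or invent a pairing. In an open study, choosing the test after the data are seen is what a pre-specified plan is meant to prevent. The between-product test under the primary endpoint and the between-group secondary aims are at stake. The within-group change from D0, which is most of the primary aim, is not affected.

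**Working it through.** The plan gives no power, effect size or expected score, so there is no stated figure to reproduce. The test name is checked against the design first. The consequences are then sized under assumptions labelled as such.

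**1. Can the named test be computed?** The evaluable group sizes are 33, 33 and 24.
- 33 vs 24: a paired calculation fails because the lengths differ. It runs only if 33 - 24 = 9 subjects are discarded.
- Both nozzles against control, 66 vs 24: 66 - 24 = 42 subjects would be discarded.
- 33 vs 33: it runs, but only on an arbitrary pairing.

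The mismatch therefore holds whether *products* means nozzle against nozzle or includes the no-spray control.

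**2. Will the fallback be reached?** This takes the plan's Shapiro-Wilk level of 0.01 and applies it per group (an assumption, since the between-product paragraph does not restate the rule). Irritation is scored 0 to 3. Suppose changes take only the values -1, 0 and +1. The number of possible count splits, leaving out the three in which all values are equal, is C(n+2, 2) - 3.

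| n | Splits | Rejected at 0.01 | Largest p |
|---|---|---|---|
| 24 | 325 - 3 = 322 | 322 | 0.0005 |
| 33 | 595 - 3 = 592 | 592 | 0.00005 |

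This enumeration needs no assumed probabilities. With wider spreads the outcome is less certain: for values -2 to +2 with assumed probabilities .10/.20/.40/.20/.10, simulated rejection is about 35% at n = 24 and 74-76% at n = 33. At the other extreme, if each subject has a 98% chance of no change, all changes are zero with probability 0.98^24 = 62% or 0.98^33 = 51%, and no test is informative.

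**3. What would an arbitrary pairing do?** The plan does not propose this; it is one way the sentence could be carried out. Assumed obstruction changes from -3 to +1:
- device .10/.25/.30/.25/.10, mean -0.30 - 0.50 - 0.30 + 0 + 0.10 = -1.00;
- comparator .02/.10/.25/.43/.20, mean -0.06 - 0.20 - 0.25 + 0 + 0.20 = -0.31;
- difference 0.69 grade.

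Simulated power at two-sided 5% (ranges are over repeat simulations):

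| Comparison | Signed rank, arbitrary pairs | Rank-sum |
|---|---|---|
| 33 vs 24 | 56-58% | 64-66% |
| 33 vs 33 | 71-72% | 71-73% |
| 66 vs 24 | 56-57% | 75-76% |

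With the device distribution in both arms, type I error is 4.7-5.2% for arbitrary pairing and 4.5-5.0% for rank-sum. Error control is not the problem.

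**4. Is the answer unique?** Each simulated trial was re-paired at random 200 times. A trial counts if its pairings give p-values on both sides of 0.05.
- 33 vs 24: 77-81% of trials under the 0.69-grade difference, and 40-42% with no difference.
- 33 vs 33: 33-38% and 12-13%.
- Median 2.5th to 97.5th percentile range of p within one trial, under the difference: 0.004-0.150 (33 vs 24) and 0.003-0.030 (33 vs 33).

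The rank-sum test gives one p-value per data set.

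**The case against.** **It is a naming slip that any competent analyst would correct.** Probably so. The within-product t-test is called paired and the between-product one is not, which suggests that the rank test's name was carried over from one paragraph to the next. The evidence is weak, however: *two-sided* describes direction, not independence, and the plan nowhere says the between-product t-test is unpaired. A probable slip still leaves the pre-specified test wrong, twice.

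**The primary aim is mainly within-group.** This stands and limits the severity. The between-product test is nevertheless listed under the primary endpoint, and the secondary aims ask for between-group comparisons.

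**The pairing figures describe an analysis the plan never states.** Fair. They illustrate a consequence under assumed distributions and do not forecast this trial. On the narrowest reading, nozzle against nozzle at 33 vs 33, they show no material power loss, only dependence on the pairing. The central point needs none of them.

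**Normality might not be rejected.** With enough distinct values it might not be. A seven-value spread from -3 to +3 with assumed probabilities .05/.10/.20/.30/.20/.10/.05 is rejected in only 9% (n = 24) and 17% (n = 33) of samples. That spread cannot arise for obstruction, where D0 must be 2 or 3 on a 0-4 scale and a change of +3 is impossible. For irritation it would need subjects starting at both ends of the scale.

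**The full document may name the right test.** Only the synopsis and flow-chart of a 64-page document were supplied. If another section does name it, the synopsis contradicts that section and needs the same edit.

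**Conclusion.** The plan is wrong as written: in both places the between-product fallback names a test that is not defined for independent groups. This follows from the design and group sizes alone and is certain for the supplied text.

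The practical size is moderate. The fallback is certain to be reached if irritation changes are confined to -1, 0 and +1 and vary at all, and is less certain otherwise. If the sentence were carried out by arbitrary pairing, the assumed obstruction scenario gives a loss of roughly 6 to 10 percentage points of power for 33 vs 24, about 20 for 66 vs 24 and essentially none for 33 vs 33, together with a verdict that can depend on row order. Type I error is not inflated. The within-product analyses stand. This should be fixed before analysis, but it does not threaten the trial.

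**What to change.** In the between-product paragraph, under both the primary and the secondary endpoints, replace the signed rank test with *Wilcoxon rank-sum (Mann-Whitney) test, exact or tie-corrected*. The tie handling matters because the scores take few values. Leave the within-product signed-rank fallback unchanged. While the sentence is open, it would help to call the t-test an independent two-sample test.

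The cost is one term in two places, plus any repeat elsewhere in the full document. Data, visits and sample size do not change, and the test is standard in the SAS v9.4 software the plan names. Whether to keep the normality check, add a three-group test or stratify by age are separate decisions and not part of this correction.

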## FLOW-CHART

Procedure (time-points)	V1	V2
Intervals	D0	D90 (+/-3)
Informed Consent	●	
Medical exam	●	
Medical background and previous treatment	●	
Clinical scoring including irritation of the ear canal	●	●
Audiogram	●	●
Dispense product and daily log	●	
Collect product and daily log		●
Subjective evaluation questionnaire		●
Adherence control, record of AE, concomitant treatments	●	●
End of study form		●

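### The count of ear affections is placed under a D90-D0 test, but the synopsis and flow-chart describe no D0 count, so its within-product change is undefined

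*Combined protocol and SAP*

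**What the plan says.** In section 1.5, Statistical methods, the secondary parameters are irritation, obstruction, audiogram result and "The number of auricular affection (such as otitis) during the use period". One rule covers all four: "For each product, a paired t-test will be used to test whether the change from baseline (D90-D0) differ significantly from 0". If a Shapiro-Wilk test rejects normality at 0.01, a signed-rank test replaces the t-test. Products are then compared on the same D90-D0 change, with this fallback: "If the normality assumption is not met, a non-parametric approach is used with a Wilcoxon signed rank test". The questionnaire is handled separately, by frequencies. The affection count has no such exception.

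Under Objectives, the source of the count is given: "Evaluation of the effect on the number of auricular affection (such as otitis) during the use period (daily log"). The lead-in to the secondary aims names both nozzles "and for control group, in comparison to the baseline (D0) and between groups".

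The flow-chart has the log dispensed at V1 (D0) and collected at V2 (D90). The nearest history item at V1 is "Medical background and previous treatment", with no count of affections and no time window. Inclusion criterion 4 does use a frequency, but of another condition: "Subjects having history of cerumen occlusion more than once a year".

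Planned evaluable numbers are 33 per nozzle. For control the plan has "1 group of 27 included subjects in order to have results on 24 subjects not using a spray (control group").

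**The concern.** A change from baseline needs the same quantity at two times. Irritation, obstruction and hearing are each measured at D0 and at D90. The affection count accumulates between those two visits and is known only at the end. A log that starts at D0 cannot contain earlier events, so the rule asks for a subtraction with one term missing.

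An analyst who has to produce the test must supply the missing term. The candidates are zero, a history taken over some window, or a statement that the test does not apply. Zero makes every change non-negative, so the test can only show worsening. A history longer than the period of use tends to show improvement when nothing has changed. In an open study this choice should be fixed before the data are seen. Otherwise a secondary result could be read as harm or benefit of the device when it reflects the fill-in rule.

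**Working it through.** **Inputs from the documents:** 33 evaluable subjects per nozzle, 24 controls, two-sided 5% level, Shapiro-Wilk check at 0.01, 90 days per subject. The documents give no affection rate and no rule for D0, and they state no figure for this endpoint to reproduce. All rates and fill-in rules below are therefore assumptions, shown over a range.

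**1. Parameter against schedule.**

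| Secondary parameter under the rule | Value at D0 | Value at D90 |
|---|---|---|
| Irritation score | yes, clinical scoring at V1 | yes, V2 |
| Obstruction score | yes, clinical scoring at V1 | yes, V2 |
| Audiogram | yes, V1 | yes, V2 |
| Number of ear affections | none described; log starts here | log total for D0-D90 |

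**2. D0 set to 0, one affection per affected subject.** All k non-zero changes are positive, so the exact two-sided signed-rank p is 2 × (1/2)^k.
- k = 5: 2/32 = 0.0625.
- k = 6: 2/64 = 0.031.

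Six affected users would therefore read as a significant increase, whatever happens in control. The binomial chance of 6 or more among 33 is 0.005, 0.11, 0.67 and 0.998 at affected shares of 5, 10, 20 and 40%. The t-test step is not reached with such data: for k ones and 33 − k zeros, the largest Shapiro-Wilk p over all k is 8.4 × 10⁻⁸.

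**3. No true change, three ways of filling D0.** Counts are Poisson with the same rate before and during use, n = 33, and the plan's rule is applied (Shapiro-Wilk at 0.01, then exact signed-rank or t-test). The first row is analytic: the probability that at least 6 subjects have a non-zero count, where each does so with probability 1 − exp(−mean). The other rows are from 4,000 simulations per cell.

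| D0 filled with | Result counted | mean 0.05 | 0.1 | 0.2 | 0.4 |
|---|---|---|---|---|---|
| 0 | significant increase | 0.005 | 0.09 | 0.57 | 0.98 |
| 90-day look-back | significant, either direction | 0.002 | 0.01 | 0.02 | 0.04 |
| 365-day look-back | significant decrease | 0.24 | 0.60 | 0.94 | 0.999 |

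The expected change explains the pattern. With D0 = 0 it equals the mean itself. With a 90-day look-back it is 0. With a 365-day look-back it is mean × (1 − 365/90), that is −0.15, −0.31, −0.61 and −1.22.

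**4. Between products.** If D0 is the same constant c for everyone, the difference in mean change is (A − c) − (B − c) = A − B, the difference in mean counts. The constant cancels, so this contrast keeps its meaning.

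**5. Precision of a direct comparison, 33 v 24.** At a common share p, the 95% half-width is 1.96 × √[p(1 − p)(1/33 + 1/24)]. This gives 0.158, 0.210 and 0.258 at p = 0.1, 0.2 and 0.4, or about 16, 21 and 26 percentage points.

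**The case against.** **The full plan may define the baseline.** The page footers show a plan of 64 pages, and the text reviewed is its synopsis and flow-chart. Prior otitis could be counted under medical background at V1. This stands as a limit: the finding is that no such count is described here, not that none exists.

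**The sizes are hypothetical.** This stands. Depending on the assumed rate, the D0 = 0 figure runs from negligible to near certainty. Nothing in the documents proposes a 12-month affection history, and the once-a-year wording concerns cerumen occlusion. A matched window shows no inflation. An analyst might also report the test as not applicable, which would do no harm. A reader might infer that the trial will report a false harm or benefit; the documents do not support that.

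**The endpoint is still usable.** A reader might infer that the count has no value or that the group comparison fails too. That goes too far, because a constant D0 cancels between products. The signed-rank fallback does not fit independent groups, but the same wording is used for the primary endpoint, so it adds nothing specific here.

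**The baseline comparison is a stated aim.** The lead-in to the secondary aims names D0 as well as the other groups, so removing the count from the change rule could drop part of an aim. Whether the lead-in reaches this endpoint is unclear, since its bullet follows a separate sentence on age groups. The fix has to leave room for a within-group change.

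**Controls may have no log.** The flow-chart combines product and log in one item, and controls receive no spray. The documents do not say that controls get the log, nor what the period of use means for them. A direct comparison cannot simply be assumed to be available.

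**Conclusion.** The point holds for the synopsis and flow-chart as supplied: the rule cannot be run as written for this count, because its D0 term is not described. The defect lies mainly in the within-product test. Its direction would be set by the fill-in choice: zero can only point upward, and a look-back longer than the period of use favours a decrease. How often this would produce a significant result cannot be said from the documents; the probabilities above rest on assumed Poisson rates and assumed fill-in rules.

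This is a should-fix matter on one secondary endpoint. Confidence is medium, because the rest of the plan might supply the missing count.

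**What to change.** - **Remove this count from the D90-D0 rule.** Compare each nozzle group with control on affections recorded over D0-D90. Use either the proportion with at least one affection (exact test, risk difference with 95% CI) or an event rate with time in study as offset.
- **State that controls also receive the daily log** and that their observation period is D0-D90.
- **If a within-group change is wanted,** record a look-back count of affections at V1 over a window equal to the period of use. If the full plan already defines one, cite it in the synopsis.

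**Cost.** If controls already receive the log, the between-group analysis needs only SAP wording. If they do not, giving it to them is a small data-collection change. The look-back count would add one item at V1. The direct comparison will be imprecise, as the half-widths above show, so it should be presented as an estimate with its interval.
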